during these testing procedures, rest breaks will be provided to the subjects as needed and as requested by the subject. Please see the adjoining flowchart for a summary of the procedures that subjects in each study cohort will undergo. Subjects will not be randomized to the 2 cohorts. Assignment to the cohorts will be based on the lab/personnel and subject schedules. A subject can participate in the 2 cohorts sequentially. Also, participants in Cohort 2, when testing hypotheses comprising a repeated-measures comparison of different gait training strategies (e.g. Hypothesis 4a evaluating effect of walking speed; Hypothesis 4b comparing FastFES versus Fast), participants may cross-over between strategies within or across gait sessions.

1) Medical Clearance:

If a subject shows interest in participation in cohort 2 of the study (18 training sessions), before participation, we will obtain written medical clearance from the subject's physician (See attached Medical Clearance form). In addition, the subject will undergo clinical assessment to confirm that they are eligible for study participation.

2) Procedures for Clinical Assessment of Walking Function and Muscle Strength:

All subjects will review and sign consent forms before clinical testing. Clinical Testing will be performed by a licensed physical therapist. Clinical testing may comprise: (1) measurement of subjects' over ground self-selected (SS) walking speed (6-meter walk test); (2) over ground walking endurance measured by the distance ambulated during the 6-minute walk test; (3) assessment of gait and dynamic balance (measured using the functional gait assessment, 4-square step test, and the Berg balance score); (4) lower extremity portion of the Fugl-Meyer score⁷⁰; (5) step activity monitoring; (6) lower extremity proprioception (in which each limb segment will be flexed or extended approximately 10 degrees and the subject will be asked to identify whether the limb is moving and in what

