Note that data from Cohort 1 (case series on FastFES gait training) as well as data that evaluate Hypothesis 4b (i.e. a repeated-measures comparison of the short-term effects of FastFES versus Fast on corticospinal excitability and gait biomechanics) will inform the methodology, planning, and sample-size estimation for a future larger clinical trial.

At the beginning and end of each training session, a “**pre-test**” and “**post-test**” may be performed. The pre- and post-tests will comprise 30-second trials of treadmill walking at the subject's comfortable or fast walking speed. By obtaining data while

training at a standardized walking speed and while training without FES, we will be able to measure differences in motor learning among these training strategies. The procedures for motion analyses to be used for pre- and post-tests are described in a separate section (Procedures for Motion Analyses). In addition, for a few sessions, in addition to the 30-second walking trials, the pre- and post-test may comprise assessment of spinal or corticospinal excitability.

During the training sessions, subjects may wear a harness suspended from the ceiling (no body-weight support) for safety. In addition, if needed, the subjects will be allowed to hold on to the hand rails during walking. For stroke survivors, heart rate will be monitored throughout the session with a heart rate sensor that is placed on the chest under clothing (Polar USA, Lake Success, NY). If heart rate exceeds 80% of their age predicted heart rate maximum, walking will be stopped until it returns to baseline. In addition, blood pressure will be monitored at each rest break. If a subject's blood pressure exceeds 190/100 mmHg, the session will be stopped and their blood pressure will be continually monitored until it returns to baseline. Subjects will rate their perceived exertion on the Borg Scale of Perceived Exertion every 6 minutes. If a subject reaches level 13 on the Borg scale (i.e. between 'Fairly Light' and 'Somewhat hard') they will be given a rest break⁷⁴.

5) Procedures for Motion Analysis:

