Corticospinal excitability will be assessed using a non-invasive technique called transcranial magnetic stimulation (TMS). TMS will be delivered using MagStim Stimulators with a double circular coil, custom-built double-cone or batwing coil (Magstim Ltd, Wales, UK). Electrical activity from muscles in response to the TMS will be collected using surface EMG electrodes attached to muscles that play critical roles during walking (e.g. quadriceps femoris, tibialis anterior, soleus, gastrocnemius, hamstrings, etc). In addition, EMG signals will be recorded from a couple of upper extremity muscles (e.g. first dorsal interosseous, flexor digitorum indicis) to be used as a control. First, the site on the scalp where a TMS pulse of ~30 to 60% maximum stimulator output produces the greatest muscle response (hotspot) will be identified for a target muscle ⁷⁶. The motor threshold intensity will be identified for the target muscle. After this, TMS intensity may be set at 120% motor threshold and motor mapping data collected as single pulses of TMS are delivered to different areas of the scalp. Subjects will wear a closely fitting cap containing 1-cm grids in antero-posterior and medio-lateral orientations. During mapping, 10 consecutive stimuli will be delivered at scalp locations at 2-cm distance intervals. Next, single TMS pulses of a range of intensities (0 to 100% maximum stimulator output) will be delivered in a random order (one pulse every 3-5 seconds) at the hotspot location for the targeted muscle. These data will be used to plot the TMS recruitment curve, i.e. the relation between stimulation intensity and the EMG amplitude. Next, the muscle's maximal contraction muscle activity level will be determined by asking the subjects to contract their muscle as hard as possible. Additionally, a paired-pulse data may be collected to determine the magnitude of intracortical inhibition and facilitation of the primary motor cortex bilaterally. TMS will be delivered using two Magstim 200² stimulators connected via a BiStim² module (Magstim Co., Wales, UK). Conditioning pulses will be delivered a range of intensities (75-155% of the active motor threshold determined for the target muscle). The intensity of the test stimulus will be set to the percentage of TMS stimulator output that elicits an MEP of 1 mV. Inhibition will be indexed with interstimulus intervals of 2 ms; facilitation at 12 ms. Twenty stimuli will be delivered for each conditioning stimulation intensity (10 conditioned at 2 ms, 10 conditioned at 12 ms). Twenty non-conditioned, single-pulse stimuli will also be delivered during the paired-pulse TMS assessment. Comparing mean peak-to-peak MEP amplitudes of the conditioned and non-conditioned stimuli will be used to index short intracortical inhibition and facilitation. Additional TMS data may be collected as the subjects maintain a low level contraction from the muscles (~10% maximal EMG level). This part of the study is optional and as part of the consent process, the subjects will be able to choose to participate in the remaining study procedures and opt out of the brain stimulation portion of the study.

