Exclusion Criteria for Post-Stroke Subjects are: 1) evidence of moderate/ severe chronic white matter disease or cerebellar stroke on MRI, 2) cerebellar signs (ataxic ("drunken") gait or decreased coordination during rapid alternating hand or foot movements, 3) insulin dependent diabetes, 4) history of lower extremity joint replacement, 5) score of >1 on question 1b and >0 on question 1c on NIH Stroke Scale, 6) inability to communicate with investigators, 7) neglect/hemianopia, or unexplained dizziness in last 6 months, 8) neurologic conditions other than stroke, 9) orthopedic problems in the lower limbs or spine (or other medical conditions) that limit walking. Additional exclusion criteria for TMS (measurement of corticospinal excitability) are: 10) history of seizures, 11) metal implants in the head or face, 12) history of recurring or severe headaches/migraine, 13) headache within the past 24 hours, 14) presence of skull abnormalities or fractures, 15) hemorrhagic stroke, 16) history of dizziness, syncope, nausea, or loss of consciousness in the past 12 months.

Inclusion Criteria for Able-Bodied Individuals are: 1) age 21 to 80 years, 2) no history of neurologic disease, 3) no history of orthopedic disease or injury affecting the lower extremity.

Exclusion Criteria for Able-Bodied Individuals are: 1) history of neurologic disease, 2) history of orthopedic disease or injury to the lower extremity, 3) an implanted cardiac pacemaker. Additional exclusion criteria for the TMS portion of the study (corticospinal excitability measurement) are: 4) history of seizures, 5) metal implants in the head or face, 6) history of recurring or severe headaches/migraine, 7) headache within the past 24 hours, 8) presence of skull abnormalities or fractures.

Subject Recruitment. Study participants will be recruited from the general community within and outside Emory University.

Withdrawal from study. Participation in the present study will be voluntary and subjects will be able to opt out of the study at any time.

Our subject population will be representative of adult patients with stroke and healthy adults. The incidence of stroke is considered rare in children, estimated to be less than 13 cases per 100,000 children⁸⁸ and their inclusion would not provide additional information compared with the data gathered in adults.

7. Statistical analysis

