Hypotheses testing will be done with a p-value set at 0.05. The outcome variables used for analyses will include peak knee and ankle flexion during walking, propulsive forces during walking, walking speed and endurance, peak and duration of EMG activation during walking, and TMS-derived measures of corticospinal excitability (peak EMG in response to TMS, motor threshold intensity, slope and peak of the TMS-recruitment curve). To test *H1*, for each of the variables, one-way repeated measures ANOVA will be performed to check for differences in the variable after versus before 18 sessions of training. To test *H2*, we will plot the dependent variable versus time (test session number). Using these plots, the time to plateau and the time when the variable first shows a positive within-session change (threshold time) will be determined. One way repeated measures ANOVA will be used to compare the time to plateau and threshold time among 3 variables – peak propulsion, peak TMS muscle response, and over ground walking speed. To test *H3*, a Pearson's correlation will be performed between the change in peak propulsion after training versus change in peak TMS muscle response after training. For the hypothesis involving within-session changes (*H4*), repeated measures ANOVA will be performed to compare the within-session percentage change for each variable between different rehabilitation strategies.

Power Analysis: The current protocol has been powered using the primary outcome measure of paretic propulsive force generation. Based on means and standard deviations from our existing pilot data, for each aim, a sample of 24 subjects will provide 80% power to detect a 4.2% difference in propulsive force between sessions with standard deviation of 6% at a two-sided alpha level of 0.05. After completion, the data from this study will be used to conduct systematic power analysis for other outcome variables, which will be utilized to design a larger-scale future study.

8. Adverse event reporting

We will notify the IRB of any adverse events that occur during the protocol.

10. Device information

Equipment for Motion Analysis and Gait Retraining: A 7-camera system will be used to collect motion analysis data (Vicon, Oxford, UK). Ground reaction forces during treadmill walking will be collected using a treadmill instrumented with two 6-component force platforms under each

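### TMS is optional and carries its own exclusions, so H2, H3 and the TMS parts of H1 and H4 rest on a selected subset of unplanned size, and the H2 ANOVA needlessly drops people without TMS from the propulsion-versus-speed comparison

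*Combined protocol and SAP*

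**What the plan says.** Section 5, subsection 8 (corticospinal excitability) makes TMS a matter of choice at consent: "the subjects will be able to choose to participate in the remaining study procedures and opt out of the brain stimulation portion".

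Section 6 gives stroke participants a separate list: "Additional exclusion criteria for TMS (measurement of corticospinal excitability) are: 10) history of seizures", running to item 16. Item 15 is hemorrhagic stroke. Able-bodied participants have five such items. The Risks text in Section 5 words the seizure and the syncope/dizziness exclusions as applying to the whole study.

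Section 7 tests H2 by a one-way repeated measures ANOVA of time to plateau and threshold time across "peak propulsion, peak TMS muscle response, and over ground walking speed". It tests H3 by correlating change in peak propulsion with change in peak TMS response. H1 and H4 (Section 4) each name corticospinal excitability beside gait biomechanics.

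On sample size, Section 7 states: "The current protocol has been powered using the primary outcome measure of paretic propulsive force generation". It then says that "a sample of 24 subjects will provide 80% power to detect a 4.2% difference in propulsive force between sessions with standard deviation of 6" per cent, and it applies this figure to each aim. The test is two-sided at alpha 0.05. Power for other outcomes is left until the study is complete. Section 4 puts 25 people in Cohort 1, stroke and able-bodied together. Section 6 allows for about 10% withdrawal.

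On timing, Section 5, subsection 4 says in its pre-test and post-test paragraph that "for a few sessions, in addition to the 30-second walking trials, the pre- and post-test may comprise assessment of spinal or corticospinal excitability". Earlier in the same subsection, Cohort 2 outcomes, corticospinal testing included, may be taken around every training session.

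**The concern.** A Cohort 1 participant may complete all 18 sessions with full gait and walking-speed data and have no TMS data, by choice or through a TMS-only exclusion. The plan has no TMS analysis set, no expected uptake and no rule for such people.

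Two things follow. First, H1 gait and function results would describe one group, while H2, H3 and the H1 TMS result would describe a narrower one, without hemorrhagic stroke among its stroke members. A reader comparing them could not tell whether a difference lies in the outcome or in the people. Second, a repeated measures ANOVA in its usual form needs every level from every person. Someone without a TMS time is lost from the whole H2 analysis, including the comparison of propulsion with walking speed, for which that person's data are complete.

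**Working it through.** **1. Who can contribute to each test**

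- H1: everyone for gait and function; only people with TMS for corticospinal variables.
- H2: the ANOVA needs three times per person, one from TMS, so only people with TMS.
- H3: one of the two correlated changes is the TMS response, so only people with TMS.
- H4: everyone for gait; only people with TMS for corticospinal excitability.

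**2. The plan's own figure**

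Inputs from Section 7: difference 4.2, SD 6, two-sided alpha 0.05, n = 24, power 80%. If 6 is the SD of the within-person difference, d = 4.2/6 = 0.70. A paired t test (noncentral t, noncentrality d√n) has power 79.9% at n = 18, 82.3% at n = 19 and 90.7% at n = 24. So 19 would do for 80%, and 24 is conservative for propulsion.

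The stated 80% at n = 24 is recovered with d = 0.597, that is, an SD of the difference of 4.2/0.597 = 7.03. With a per-session SD of 6, SD_diff = 6√(2(1 − ρ)), which gives ρ = 1 − 7.03²/72, or about 0.31. The text states no such correlation, so both values of d are carried below.

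**3. Size of the TMS subset in Cohort 1**

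Uptake u is an assumption, shown as a range. It covers opt-out and TMS ineligibility together. n = 25u, rounded down. For H3, the correlation detectable with 80% power by Fisher z is r = tanh[(1.960 + 0.842)/√(n − 3)]. For example, n = 22 gives tanh(2.802/√19) = 0.567 and n = 15 gives tanh(2.802/√12) = 0.669. The power columns borrow the propulsion effect size, which is a further assumption.

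| Uptake | n | Detectable r (H3) | Paired power, d = 0.70 | Paired power, d = 0.597 |
|---|---|---|---|---|
| 100% | 25 | 0.535 | 91.9% | 81.7% |
| 96% | 24 | 0.545 | 90.7% | 80.0% |
| 90% | 22 | 0.567 | 87.9% | 76.2% |
| 80% | 20 | 0.591 | 84.4% | 71.7% |
| 70% | 17 | 0.634 | 77.3% | 63.8% |
| 60% | 15 | 0.669 | 71.3% | 57.6% |

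Keeping 24 of 25 needs 24/25 = 96% uptake. The table treats 25 as the number left after withdrawal. If 10% must still come off, the subset is 25 × 0.9 × (0.6 to 0.9) = 13.5 to 20.25.

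**4. The avoidable part of the loss in H2**

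Propulsion versus walking speed needs two times per person, neither from TMS. The ANOVA as written runs it on 15-22 people where up to 25 have the data, so 3-10 people are discarded. At d = 0.70, that takes power from 91.9% to 71.3-87.9% for a comparison that TMS uptake need not touch.

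**The case against.** The strongest reply is that Section 7 never sized the study on TMS. It powers propulsion, defers other outcomes, and Section 5 calls Cohort 1 a case series to inform a later trial. That stands. A reader might infer that 24 is the planned TMS sample, because the figure is given for each aim and both aims name corticospinal excitability. The wording ties it to propulsion, so the gap is an unplanned TMS number, not a shortfall against a plan.

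It is also fair that low TMS power is not shown. No uptake is given, the effect size is borrowed from propulsion, and at d = 0.70 about 19 people with TMS would still give 80%. Cohort 1 also includes able-bodied people, who have fewer TMS exclusions.

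Three further readings are tempting and unsupported:

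- That people with a history of seizures or syncope can enter Cohort 1 and merely skip TMS. Section 6 lists these items as TMS exclusions, but the Risks text words them as study-wide. If they are study-wide, five of the seven stroke items remain specific to TMS, hemorrhagic stroke among them. The passages must be reconciled.
- That most H4 corticospinal contrasts will lack complete pairs. Subsection 4 allows Cohort 2 testing around each session in one place and at a few in another, both as options. Timing is unfixed; missing pairs are not shown. Few sessions also limit time points, not people.
- That Cohort 1 should be reserved for people who accept TMS, since "Assignment to the cohorts will be based on the lab/personnel and subject schedules". That would tie the 18-session training to brain stimulation, against the opt-out in subsection 8, and would narrow the population for the primary propulsion outcome.

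None of this answers the point about H2: the chosen ANOVA discards usable propulsion and speed data.

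**Conclusion.** The concern holds in this form. H2 and H3 as analysed, and the TMS parts of H1 and H4, rest on a self-selected and medically restricted subset with no planned size, and the H2 ANOVA spreads that restriction to a comparison that does not need TMS. The gait part of H4 is unaffected.

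The selection and the loss of data in H2 follow from the text, given the usual complete-data form of the ANOVA. Their size does not: the 15-22 people rest on an assumed 60-90% uptake of 25, and the power figures also on d = 0.70. On those assumptions the effect is moderate. H3 could detect only correlations of about 0.57-0.67 or larger, against 0.545 at n = 24, and paired power would be 71-88%, against 91%.

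**What to change.** In Section 7:

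1. Analyse H2 with a mixed model (outcome type as fixed factor, participant as random effect) or with separate paired contrasts, so that people without TMS stay in the propulsion-versus-speed comparison.
2. Report the H1 gait and function results for the TMS subset beside the full cohort, with the number of people in each, so that H1 can be read against H2 and H3 in the same people.
3. State that the TMS contrasts in H2, all of H3 and the H1 TMS conclusions apply to TMS-eligible participants who consent to TMS.

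In Section 5, subsection 4, reconcile the two statements on how often corticospinal excitability is measured in Cohort 2. If it is measured at only some sessions, place it before and after both sessions of the FastFES-versus-Fast comparison, which that subsection already singles out for corticospinal excitability. Also reconcile the Risks text with Section 6 on the seizure and syncope/dizziness exclusions.

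The cost is slightly more analysis work and some rewording. Allocation to cohorts and the voluntary status of TMS do not change. A mixed model does not remove the selection: its TMS contrasts still rest on who had TMS, which is why item 3 is needed.

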A subset of the able-bodied individuals may also be requested permission to utilize a brain MRI scan has already been obtained as part of a different IRB protocol. The IRB protocols that we are requesting permission to use the brain MRI scans from are two protocols whose PI ([name]) is a co-investigator in the current IRB protocol: IRB00081268 (Noninvasive brain stimulation to evaluate neural plasticity after stroke) and IRB00072542 (Using concurrent brain imaging and stimulation to characterize brain behavior in stroke). The subjects will already have undergone an MRI as part of the other study protocol and if they volunteer for our study protocol, we will be able to capitalize on the MRI brain scan data obtained as part of the study to add valuable information to the current study data. This will also enable us to customize the brain stimulation to the individual's brain anatomy (for the subset of able bodied participants who have the MRI scan) and conduct a preliminary study analysis to assess correlations between brain imaging data, brain stimulation data, and walking function/biomechanics. The ability to utilize these existing MRI scans will add considerably to the depth and wealth of data collected as part of the current study without adding to subject's risks, discomfort, or time/effort. The brain scans will be used to evaluate preliminary relationships between brain structure (measured using the MRI images), walking function (measured during single or multiple sessions involving walking tasks in the gait lab), and brain excitability (measured during the brain stimulation sessions).

3. Introduction and Background:

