published using single-pulse TMS; only 2 cases of seizures have been reported with single-pulse TMS⁸¹⁻⁸³. In addition, Gilbert et al showed that in 38 studies involving 850 subjects including children with cerebral palsy and other neurological conditions, there were no seizures or other major adverse events⁷⁷. Another recent review concluded that the safety of single-pulse TMS in clinical practice, including as an acute migraine headache treatment, is supported by biological, empirical, and clinical trial evidence⁸⁰. TMS rates used in our study, of 0.2 Hz or less, are safe in epileptic patients⁸⁴. However, to take additional steps to minimize risks, we will not include any individuals with a history of seizures in our study. In addition, during TMS, subjects may feel twitches in the muscles of arm, leg or face during the magnetic stimulation, but these twitches should not be painful. There is a rare possibility of headaches, scalp discomfort, dizziness, or light-headedness. If they occur, these effects are usually mild and short-lasting. Recently, a research of literature showed recent publications providing case reports of episodes of syncope or seizure during single-pulse TMS in able-bodied individuals⁸⁵⁻⁸⁷. To prevent the risk of syncope, vaso-vagal stimulation, or dizziness in the current study, we will exclude subjects if they have a history of syncope, dizziness, loss of consciousness, or nausea in the past 12 months, including but not limited to syncope triggered by drawing blood. Metal and conductive objects close to the coil may move during magnetic stimulation. A click during magnetic stimulation may be heard. The subjects may be provided with foam earplugs that can prevent any discomfort from this clicking noise. There is also a risk of mild skin redness or irritation at the location where the muscle sensors have been placed, but this will usually go away quickly after sensors are removed.

Risks associated with assessment of muscle strength include fatigue, muscle soreness, strains in the muscles surrounding the hip, knee, ankle or foot.

Potential Benefits

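### The able-bodied TMS exclusion list omits the syncope and dizziness criterion that the Risks section adopts because of able-bodied case reports

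*Combined protocol and SAP*

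**What the plan says.** Section 5, Risks (TMS), refers to recent "case reports of episodes of syncope or seizure during single-pulse TMS in able-bodied individuals". To prevent fainting and similar events it then states that "we will exclude subjects if they have a history of syncope, dizziness, loss of consciousness, or nausea in the past 12 months", and adds that fainting provoked by blood drawing counts. The sentence speaks of subjects generally.

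Section 6 sets out the eligibility criteria in separate lists.

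- Stroke: "Additional exclusion criteria for TMS (measurement of corticospinal excitability) are: 10) history of seizures, 11) metal implants in the head or face". The list ends with "15) hemorrhagic stroke, 16) history of dizziness, syncope, nausea, or loss of consciousness in the past 12 months".
- Able-bodied: "Additional exclusion criteria for the TMS portion of the study (corticospinal excitability measurement) are: 4) history of seizures". The list ends with "7) headache within the past 24 hours, 8) presence of skull abnormalities or fractures". The general able-bodied exclusions (items 1-3) cover neurologic disease, lower-limb orthopedic disease or injury, and a cardiac pacemaker.

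TMS in able-bodied people is planned. Of the use of existing MRI scans, Section 2 says "This will also enable us to customize the brain stimulation" to individual anatomy "for the subset of able bodied participants who have the MRI scan". It also describes methodology experiments in able-bodied participants, with standing and seated posture among the parameters of interest.

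On pulse rate, Section 5, item 8, spaces recruitment-curve pulses 3-5 s apart. Risks gives the study's rate once as strictly below 0.2 Hz and once as at or below 0.2 Hz. It describes the TMS as single-pulse, whereas item 8 also allows paired pulses.

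**The concern.** The two sections give different answers to one eligibility question: may an able-bodied volunteer who fainted within the past year have TMS? Risks says no; the numbered able-bodied criteria raise no bar. The gap falls on the group whose case reports are the stated reason for the rule.

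The list carries real weight for these participants. Section 5 says clinical testing of able-bodied subjects may be reduced or omitted. It ties the stress test to Cohort 1 and medical clearance to an 18-session cohort. For an able-bodied person in a one-session pilot experiment, the documents describe no other medical check. If TMS were given standing, a faint could also mean a fall; that is an inference, and the documents report no such event.

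The rate mismatch is a smaller matter. An operator following the procedure as written could exceed the rate on which the Risks text relies.

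**Working it through.** **1. Matching the two TMS exclusion lists in Section 6**

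| Content | Stroke item | Able-bodied item |
|---|---|---|
| Seizure history | 10 | 4 |
| Metal in head or face | 11 | 5 |
| Recurrent or severe headache, migraine | 12 | 6 |
| Headache in the previous 24 h | 13 | 7 |
| Skull abnormality or fracture | 14 | 8 |
| Hemorrhagic stroke | 15 | cannot apply |
| Dizziness, syncope, nausea or loss of consciousness, 12 months | 16 | **absent** |

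Stroke TMS items: 7. Less the one that cannot apply: 7 − 1 = 6. Present in the able-bodied list: 5. Missing: 6 − 5 = 1, which is item 16. Able-bodied items 1-3 do not supply it, since a simple faint need not count as neurologic disease.

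Risks makes two TMS exclusion commitments. The one on seizures reaches both lists (items 10 and 4); the one on syncope reaches only the stroke list. No reason is given for the difference.

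**2. How many people it could touch**

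Inputs: 15 able-bodied people in the planned MRI subset (Section 5, MRI procedures) and 45 able-bodied people to be recruited (Section 6). The frequency of a qualifying history is not given; 5-20% is assumed.

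- 15 × 0.05 = 0.75 and 15 × 0.20 = 3, so about 1-3
- 45 × 0.05 = 2.25 and 45 × 0.20 = 9, so about 2-9

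These counts take the able-bodied list as the only screen and assume that everyone in the group has TMS, although item 8 makes TMS optional.

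**3. Pulse rate (secondary)**

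Rate in Hz = 1 / interval in seconds. The stated ceiling is 0.2 Hz.

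| Interval | Rate | Ratio to 0.2 Hz | Below 0.2 Hz? | At most 0.2 Hz? |
|---|---|---|---|---|
| 3 s | 0.333 Hz | 1.67 | no | no |
| 4 s | 0.250 Hz | 1.25 | no | no |
| 5 s | 0.200 Hz | 1.00 | no | yes |

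The stated rate is therefore not reproduced from the procedure. Only an interval of exactly 5 s meets the looser statement, and no interval in the range meets the stricter one.

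**The case against.** The strongest reply is that the exclusion is already in the protocol. The Risks sentence covers all subjects and binds the investigators, so what is missing is a repetition and not a safeguard. The documents do not show which text screeners use, and nothing proves that anyone was or would be wrongly admitted. This is correct as far as it goes, and it limits what can be said about harm. It does not remove the conflict: the able-bodied list, followed as written, lets through a person whom Risks excludes.

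Three further objections have force.

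- The 5-20% range has no source in the documents, and the counts fall to zero if Risks is applied to everyone. The 15 is not a firm minimum of able-bodied TMS recipients, because Section 2 says only that permission to use scans may be sought. The counts are illustrative, and the finding does not depend on them.
- The fall scenario is speculative: Section 5, item 8, gives no posture for the TMS session. It is not needed for the conclusion.
- On pulse rate, the documents do not show 0.33 Hz or paired pulses to be unsafe, and the Risks wording may be the part that is wrong. Correcting either text would resolve that mismatch.

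**Conclusion.** The concern holds. The able-bodied TMS list lacks one of the six applicable exclusions, and it is the one that Risks adopts on the strength of able-bodied case reports. This is an internal inconsistency in participant-safety text, read directly from the two sections and independent of any assumption about frequency. It should be corrected because a stated safety commitment is not carried into the able-bodied eligibility list. How many people it would affect is unknown: about 1-9 across the two groups under the assumed 5-20%, and none if Risks is applied in practice. The power calculation and analyses in Section 7 are not involved.

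The rate discrepancy (up to 1.67 times the stated 0.2 Hz) and the silence of Risks on paired-pulse TMS are also real, but they are minor points of accurate description.

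**What to change.** Add item 9 to the able-bodied TMS exclusions in Section 6, with the same content as stroke item 16. It would be better still to add the Risks clarification about fainting at blood draws to both lists, so that all three texts agree.

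The cost is one line and a wording amendment. Any volunteers newly screened out (about 1-9 under the assumption above) are lost to TMS only.

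For the secondary points, set the recruitment-curve interval to at least 5 s and state the rate as at most 0.2 Hz in both places in Risks. Alternatively, keep 3-5 s and restate the rate as up to about 0.33 Hz, checked against the safety guidance that the protocol says it follows. The longer interval adds on average 5 − 4 = 1 s per pulse. The number of pulses is not given; assuming 40-100, that is 40-100 s, or about 0.7-1.7 minutes per curve. If paired-pulse TMS is kept, name it in Risks.
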